**Table 9-1 Data Collection Schedule**

Procedure/ Assessment	Enrollment Visit	Baseline Visit (Day 0)	Interim Medical Record Review  (150-210 days)	Final Clinic Visit  (350-430 days)
Informed Consent Process, including Signature and Date	X	--	--	--
Inclusion/Exclusion Criteria Assessed	X	--	--	--
Confirmation LATITUDE Transmission	--	X	--	X
Device Information	--	X	X (changes only)	X (changes only)
Distribute Subject ID Card with Site Contact Information	--	X	--	--
Sleep Incline Calibration	--	X	--	--
Demographics	--	X	--	--
Physical Assessment	--	X	--	X
Medical History	--	X	--	--
Blood Labs	--	O	--	O
Cardiac Medications Reviewed	--	X	--	--
Assessment of Adverse Events and Reviewable Clinical Events	--	X	X	X
Supplementary Diagnostics Data Collection	--	--	O	O

 The interim medical record review does not require an in-clinic visit.

\*Please complete the final clinic visit form for subjects withdrawn prior to 350 days

An "X" indicates a mandatory data requirement. Failure to complete will result in a protocol deviation.

An "O" indicates optional but recommended data.

## 9.2 Device Interrogation / Collection of Programming Data

The device must be interrogated with a PRM at enrollment, baseline and during the final clinic visit. These interrogations are required to confirm the appropriate programming of the device, including Heart Failure Sensors ON, Sleep Incline Sensor ON, and Respiratory Sensor ON. All other device settings can be programmed per clinician discretion. The PRM must also be used to calibrate the Sleep Incline Sensor.

HF Sensor data and Sleep Incline data will be collected via the LATITUDE patient communicator.

### **9.3 Study Candidate Screening**

Subjects will be recruited from the investigator's pool of patients that have an ICD or CRT-D implant with the HeartLogic feature. The investigator has the responsibility of screening potential subjects and selecting only those who meet the eligibility criteria. For the purpose of this clinical study no screening logs are required, and the site is not required to report screen failures.

### **9.4 Strategies for Recruitment and Retention**

Study recruitment will rely upon the general pool of patients that meet the eligibility criteria and have an ICD or CRT-D implant.

### **9.5 Informed Consent**

Eligible subjects can be consented for the study any time after the calendar day of the ICD or CRT-D implant. Participants who meet all the inclusion criteria and none of the exclusion criteria, and sign and date the informed consent form are considered enrolled in the study. No procedures or data will be collected prior to signing the informed consent form. Legal Authorized Representatives (LAR) must not be used for this study.

#### **9.5.1 Data Linkage**

The PREEMPT-HF study will also link study data to third-party data sources. The purpose of data linkage is to conduct research to improve clinical applications such as patient management and therapy (both device and non-device), algorithms for patient risk stratification and prognostic evaluation, health economic evaluation, and clinical trial methodologies. Data linkage will focus on disease states and comorbidities common in device patients such as heart failure, hypertension, cardiac arrhythmias, acute coronary syndrome, heart valve disorders, respiratory disease, renal disease, gastrointestinal disease, sleep apnea, infectious disease, etc.

PREEMPT-HF study data will be used in combination with internal BSC databases (e.g., device tracking database) to obtain, use, and disclose certain protected health information to third-parties. This may include device serial and model number, implant date, the hospital where the implant procedure was performed, subject last name, date of birth, address zip code, and the last four digits of the subject's social security number.

The third-party data sources include but are not limited to payer administrative claims and health analytics (e.g., Centers for Medicare and Medicaid Services, Truven, Optum), provider electronic health records (EHRs), pharmacy benefit management (or other third-party administration of prescription drug programs), clinical registries (used for post market surveillance or quality improvement), biobanks, and government databases (such as census data, or social security death index).

The subject may withdraw permission for the use and sharing of personal health information at any time if provided in writing to the study doctor. Please notify Boston Scientific of any subjects that submit in writing their request to withdraw their permission for the use of personal health information.

Boston Scientific will abide by all applicable laws, regulations, and data use agreements associated with data linkage to third-party data sources. This research could not practicably be conducted without access to and use of the protected health information. Additionally, Boston Scientific will employ reasonable administrative, physical and technical safeguards that are designed to protect against data loss, misuse of data, unauthorized access or disclosure of data, and alteration or destruction of data. This includes implementation of adequate plans to use only minimum identifiable data needed in a finder file to enable linkage, and the removal and destruction of the finder file after each linkage is complete at the earliest opportunity consistent with conduct of research.

### ***9.6 Enrollment Visit***

Enrollment cannot occur on the same calendar day of the implant procedure, but may occur before the patient is discharged from the hospital where the implant occurred.

At the enrollment visit the following activities are required:

- Confirmation of subject consent
- Confirmation that the subject meets all the inclusion and none of the exclusion criteria (Sections 7.2 and 7.3)

### ***9.7 Baseline Visit [Day 0]***

The baseline visit must be conducted no sooner than seven (7) days post-device implant to allow for automatic initialization of the Sleep Incline Sensor. Enrollment and baseline visits can be completed on the same day provided the device has been implanted for at least seven (7) days with the Sleep Incline Sensor turned ON. However, the baseline visit must be conducted no later than 30 days following enrollment.

The following information must be gathered and entered into the eCRFs in a timely manner.

- Subject device information
  - Manufacturer, model and serial number of pulse generator and active leads
  - Implant date for all active devices
  - Anatomical locations of pulse generator and leads
- LATITUDE monitoring
  - Confirm that the subject is monitored in LATITUDE
  - Review in LATITUDE at the patient level that HeartLogic is disabled
  - Confirm scheduled remote patient monitoring follow-ups are programmed to occur at a frequency no less often than once every three (3) months.

- Sleep Incline Sensor calibration and data collection:
  - \*Important: The device will NOT collect any Sleep Incline data until a body calibration has been performed. Calibration is a required step to ensure the PG is collecting sleep incline data.\**
  - Sleep Incline Sensor calibrations are performed by the clinician using the PRM. Calibration should be performed using the two-position method for increased accuracy. This requires the patient to sit and to lie down, so the calibration must be conducted in a room with adequate facilities. Care must be taken to ensure that the subject is fully vertical or horizontal when the PRM captures the upright and supine postures. Once the patient is in position, the clinician will run the software on the PRM for the data collection. It takes approximately 10 seconds of data collection for each position. The entire procedure should take about 1-2 minutes. For patients unable to perform the two-position calibration, a single position may be performed.
  - Regardless of whether the Sleep Incline Sensor has been calibrated prior to the PREEMPT-HF Study baseline visit, please re-calibrate. Document the calibration in the patient medical record.
  - If the Sleep Incline Sensor is turned ON, but the Sensor initialization is incomplete seven (7) days after implant, then calibration cannot be performed. Please document in the eCRF if initialization failure resulted in the inability to calibrate the sensor. If initialization failure occurs, calibration may be performed at a subsequent standard of care office visit.
  - Record the details of the sleep incline calibration in the patient medical record as source documentation.
- Provide subject with an ID card containing PREEMPT-HF study site contact information. Subjects should be instructed to inform the study coordinator or any other study site personnel if they are hospitalized for any reason, or receive IV HF treatment)
- Subject demographics (see Appendix for details)
- Physical assessment (Appendix)
- Medical history (Appendix)
- Enter all cardiac medications
- Blood labs: If available in the medical records, enter the most recent blood lab values collected for the following:
  - Natriuretic peptides (BNP or NT-proBNP) and date of collection
  - Creatinine and date of collection
- Indicate if the subject is implanted and monitored using a commercial pulmonary artery pressure sensor, or if the subject is monitored using serial natriuretic peptides.
- Review subject medical records since the enrollment and assess for Reviewable Clinical Events (RCEs) and reportable AEs (See Figure 3).

In addition, subjects located in the United States (US) who own a smart phone may be provided with the option to use a geo-location tracking app to ensure timely reporting of hospitalizations. The app contains the location of all hospitals in the US. If a subject exceeds the pre-specified and programmable amount of time at a hospital, the app will prompt the patient to confirm a hospitalization. In addition, the investigational site will get a notification that the patient may be hospitalized. To protect patient privacy, Boston Scientific will not receive these notifications.

### **9.8 Interim Medical Record Review [150-210 days]**

The interim medical record review must be conducted 150 to 210 days following the baseline visit. It is encouraged to perform the interim medical record review at the time of an in-clinic standard of care visit. If this review coincides with an in-clinic visit, the subject must be asked whether he or she had any reviewable clinical events (RCEs) since the baseline visit. As defined in section 5.1, an RCE is defined as either an all-cause hospitalization, or HF outpatient visit. If the subject reports having an RCE at a center not participating in the study, every effort should be made to obtain medical records from the center. An overview of the activities and data to be collected is provided below.

- Review subject medical records since the date of the baseline visit and assess for RCEs and reportable AEs
- If RCEs are identified during the medical record review (see Figure 3 for details), complete the “Reviewable Clinical Event” eCRF.
  - Each newly identified RCE must have a unique eCRF. For example, if the subject had two HF outpatient visits for an on-going AE it must be captured in two separate “Reviewable Clinical Event” eCRFs.
  - If a single RCE is associated with multiple AEs, only the primary AE (i.e., the chief complaint leading to the clinic/hospital visit) should be associated with an “Reviewable Clinical Event” eCRF. For example, if a subject was admitted due to symptoms of gastrointestinal bleeding but developed worsening HF during the course of hospitalization, the gastrointestinal bleeding would be the primary AE, and therefore it would be associated with the “Reviewable Clinical Event” eCRF. A separate “Reviewable Clinical Event” eCRF is not required for the in-patient worsening of HF even if it is reported as a separate AE.
- For hospitalizations, the Principal Investigator must review the patient’s medical records and classify the primary organ cause in the “Reviewable Clinical Event” eCRF (see Appendix for details). Appropriate classification is important for event subgroup analysis. Classification also triggers the request for medical record documentation to be sent to BSC.
- Supplementary diagnostics data collection: This eCRF sub-folder is created only if the investigational site confirms that the subject is routinely monitored using pulmonary artery (PA) pressure data from an implanted commercially-approved device, or using serial natriuretic peptides (BNP or NT-proBNP). If the site

confirms the use of supplementary diagnostic data, the following should be entered in the corresponding eCRF:

- PA pressure readings
- Serial natriuretic peptide values
- Volume status of the subject (hypervolemic, hypovolemic, euvolemic)
- Treatments initiated in response to the diagnostic data

*\*\*The sponsor retains the right to restrict the total amount of supplemental data that would be collected during the course of the study. In this event, sites would be notified to stop reporting supplemental data, and the data base eCRF may be locked for further data entry.\*\**

### **9.9 Final Clinic Visit [350-430 days]**

The final visit must be performed in-clinic 350 to 430 days following the baseline visit. If the patient is withdrawn prior to the window for the final clinic visit, please complete the final clinic visit at the point of withdrawal. An overview of the data to be collected at this visit is provided below.

- Review subject medical records since the date of the baseline visit and assess for RCEs and reportable adverse events.
  - Collect and report using the same process used in the interim medical record review (See section 9.8).
- Physical assessment (See Appendix)
- Blood labs: Enter the most recent blood lab values since the baseline visit for the following.
  - Natriuretic peptides (BNP or NT-proBNP) and date of collection. If serial natriuretic peptide data has already been entered in the supplementary diagnostics form, the same values need not be entered in the final visit eCRF.
  - Creatinine and date of collection
- Supplementary diagnostics data collection:
  - Collect using the same process as in the interim medical record review (See section 9.8).
- Interrogate the device with a PRM. This ensures that the device data will be uploaded when the patient returns to within range of the communicator.
- Confirm that a LATITUDE transmission occurred in the previous 90 days. If transmission has not occurred instruct patient to do a patient initiated interrogation when they are in range of their communicator.
- Remote monitoring usage:
  - Provide information about the frequency and use of remote monitoring to manage the patient's HF condition over the past 12 months (e.g. sleep incline, weight, blood pressure, arrhythmia burden).

### 9.10 Study Completion

An “End of Study” eCRF must be completed when the subject’s participation concludes for one of the following reasons:

- The subject completes the final in-clinic visit after 350 days (minimum final clinic visit window). At this point, the subject will exit the study, and device settings can be configured per clinician discretion. The subject status will be “completed study.”
- The subject withdraws from the study. At this point, the subject will exit the study, and device settings can be configured per clinician discretion, and the subject status will be “withdrawn”. All applicable eCRFs (including the Final Clinic Visit if possible) and the “End of Study” eCRF must be completed with information up to the point of withdrawal. Complete a review of the medical records for RCEs to the point of withdrawal, and interrogate the PG (See section 9.9 for visit details). PG interrogation ensures that the device data will be uploaded when the patient returns to within range of the communicator.
- The study is terminated by Boston Scientific. At this point, the subject will exit the study, and device settings can be configured per clinician discretion. The subject status will be “withdrawn.”

### 9.11 Source Documents

The following tables detail the data collection and the required source documentation.

#### 9.11.1 Enrollment Visit

Data Collection	Source Documentation
Informed Consent	Study Center
Inclusion/Exclusion Criteria	Study center
Confirmation of LATITUDE Enrollment	LATITUDE printout at the Study Center
Confirmation of Heart Failure Sensors ON, Sleep Incline Sensor ON, and Respiratory Sensor ON	Study Center (documented in the patient medical record)

#### 9.11.2 Baseline Visit

Data Collection	Source Documentation
Confirmation of LATITUDE transmission and HeartLogic is disabled	LATITUDE printout at the Study Center
LATITUDE Remote Scheduled Follow-up Programming	LATITUDE printout at the Study Center

Sleep Incline Sensor calibration	Study Center (documented in the patient medical record)
Demographics, Medical History, Physical Assessment, Blood Labs	Study Center
Assess for RCEs and reportable AEs	Retain original at study center and submit a copy to Boston Scientific (see Section 9.11.5 for additional details regarding RCEs)

### 9.11.3 Interim Medical Record Review

Data Collection	Source Documentation
Assess for RCEs and reportable AEs	Retain original at study center and submit a copy to Boston Scientific (see Section 9.11.5 for additional details regarding RCEs)
Supplementary Diagnostics Data	Study Center

### 9.11.4 Final Clinic Visit

Data Collection	Source Documentation
Assess for RCEs and reportable AEs	Retain original at study center and submit a copy to Boston Scientific (see Section 9.11.5 for additional details regarding RCEs)
Physical Assessment	Study Center
Blood Labs	Study Center
Supplemental Diagnostics	Study Center
Remote Monitoring Usage	Study Center

### 9.11.5 Reviewable Clinical Events

Table 9-2 summarizes specific source data requirements for the RCEs, along with the additional required reporting of all SAEs. It is preferable that original source documents are maintained on site. In lieu of original source documents, copies are required to be maintained.

**Table 9-2 Source Documentation Requirements for Reviewable Clinical Events**

Clinical Events		Source Document(s) Medical records	Disposition Options
REVIEWABLE CLINICAL EVENTS	All-Cause Hospitalizations	Cardiac hospitalizations	Upload into RAVE or Email to [contact] or [contact]
		Non-cardiac hospitalizations within 90 days of discharge from a previous HF Hospitalization (i.e., 90-day readmission)	
		Non-cardiac hospitalizations where HF was secondary contributing cause, or where inpatient worsening of HF occurred	
		Non-cardiac pulmonary or renal events	
		All other Non-cardiac hospitalizations	
	HF Outpatient Visits (with decongestive IV therapy)	
 
Physician notes
 
Medications
 
Blood lab reports
 
Further documentation may be requested by BSC
 
	
All Other AEs as required by the protocol (section 17)	
 
Further documentation may be requested by BSC
 
		

## 10 Statistical Considerations

### 10.1 Primary Endpoint

There are no primary endpoints or formal hypotheses, as the purpose of this study is exploratory. The primary objective is to investigate the association between HF Sensor data and 30-day HF readmissions.

#### 10.1.1 Hypotheses

There are no formal hypotheses. The purpose of this study is exploratory.

#### 10.1.2 Sample Size

Approximately 3750 enrollments will be required for this study. The sample size was determined based on the estimated number of HF index hospitalizations and 30-day HF readmissions needed to evaluate the primary objective. Final sample size will be determined by an interim analysis as described in Section 10.9. An index HF hospitalization refers to the first HF hospitalization during the study follow-up period. A HF hospitalization is deemed usable if sensor data is available during the event and sufficient follow up time is recorded to determine if a readmission occurs.

A total of 215 usable index HF hospitalizations are required to have at least 80% power to detect a standardized difference of 0.5 in the mean sensor change (admission – discharge) between the groups with and without a 30-day HF readmission. It is expected that of the 215 index HF hospitalizations, 43 will be followed by a 30-day readmission (20%).

A total of 215 usable index HF hospitalizations was determined based on the following assumptions:

- 80% Power to detect a standardized mean difference of 0.5 between groups
- Two-sided type I error (alpha) of 0.05
- 3:1 ratio of group sizes (no-readmission : 30-day HF readmission), where the no-readmission group will exclude index HF hospitalizations with 31 to 60-day readmissions

Assuming a 20% loss of usable HF events due to proximity to study start and exit (completion or withdrawal), a total of 270 index HF hospitalizations are required to obtain 215 usable HF hospitalizations.

Approximately 3750 enrollments are required to obtain the 270 required index HF hospitalizations. This was determined based on the following assumptions:

- 9 % index HF hospitalization rate per patient year
- 20% death/withdrawal rate throughout duration of study
- Average of 12 months of sensor data per subject

### **10.1.3 Statistical Methods**

The primary objective will be evaluated using an independent two sample t-test. A comparison of mean sensor value change (admission – discharge) will be made between the no-readmission group and the 30-day readmission group. All subjects with a usable index HF hospitalization and all subjects with a 30-day HF readmission will be included in the primary analysis. Subjects with a 31-60-day HF hospitalization will be excluded from the analysis. A two-sided alpha of 0.05 will be used.

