### 5.1 Primary Objective

The primary objective of the PREEMPT-HF study is to investigate the association between HF Sensor data and 30-day HF readmissions.

Subjects will be followed for approximately 12 months to collect the required number of clinical events to support the study objectives. These events are called Reviewable Clinical Events (RCEs), and include all-cause hospitalizations and HF outpatient visits (as defined below).

[figure not shown]
RCEs require the investigational site to review the subject's medical records and complete the appropriate eCRF (Figure 3).

Clinical events for the purposes of data analysis are defined as follows:

- **Hospitalization (all-cause):** the subject is admitted to inpatient hospital care and discharged on a different calendar date.
- **HF Hospitalization:** the subject is admitted with signs/symptoms of congestive heart failure (CHF) and receives unscheduled augmented HF therapy with oral or intravenous medications, ultrafiltration therapy or other parenteral therapy.
- **HF Readmission (30-day):** the subject is admitted for an unplanned hospitalization for any cause within 30 days post discharge from a HF hospitalization.
- **HF Outpatient Visit:** the subject has signs/symptoms of congestive HF, and receives unscheduled intravenous decongestive therapy (e.g., IV diuretics, IV inotropes, IV vasoactive drugs, ultrafiltration), in a setting that does not involve a hospitalization (e.g.: emergency room, HF clinic, primary care clinic, etc.).

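### The primary comparison drops subjects readmitted in days 31 to 60, so it does not estimate the 30-day contrast that the objective names

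*Protocol*

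**What the plan says.** Protocol 5.1 sets the primary objective as to "investigate the association between HF Sensor data and 30-day HF readmissions". The Synopsis (Statistical Test Method) and the power sentence in 10.1.2 both describe the comparison as one between subjects with and without a 30-day readmission.

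The exclusion appears in three sections of the body, in three forms:

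- 10.1.2, in the assumption on the 3:1 group ratio (repeated in the Synopsis): "where the no-readmission group will exclude index HF hospitalizations with 31 to 60-day readmissions".
- 10.1.3, on the primary test: subjects with an HF hospitalization in days 31 to 60 "will be excluded from the analysis. A two-sided alpha of 0.05 will be used".
- 10.5.1, on the primary analysis set: the same rule for HF hospitalizations, but with the window starting at day 30.

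In both 10.1.3 and 10.5.1 the sentence just before the exclusion says that every subject with a usable index HF hospitalization is included. The protocol gives no reason for the exclusion and no analysis that keeps these subjects.

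The planning statement is "A total of 215 usable index HF hospitalizations are required to have at least 80% power", with 43 of the 215 (20%) expected to be readmitted within 30 days.

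**The concern.** For a question about 30-day readmission, the comparator is everyone with a usable index event who is not readmitted by day 30. The plan removes part of that comparator using an outcome that occurs after the 30-day window has closed. Section 3.1 gives the purpose as detecting readmission and stratifying patient risk. In that use, nobody standing at discharge can set aside the patients who will return in days 31 to 60.

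The test therefore compares 30-day readmission with no readmission to day 60, while the text describes it as with versus without a 30-day readmission. If the removed subjects resemble the 30-day group in part, the reported difference is larger than the one the objective asks about. A reader would then take it as better separation at discharge than the sensors give.

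**Working it through.** **Inputs from 10.1.2.** Two-sided alpha 0.05; "80% Power to detect a standardized mean difference of 0.5 between groups"; group ratio 3:1; 215 usable index events; 43 with a 30-day readmission.

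**Assumptions.** The protocol gives no sensor mean for subjects readmitted in days 31 to 60. Let their mean lie a fraction m of the way from the no-readmission mean to the 30-day-readmission mean, with m varied. The within-group SD is 1.

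**1. The plan's own figure.** At 3:1, 43 readmitted means 3 × 43 = 129 in the comparator. The noncentrality is 0.5 × √(43 × 129 / 172) = 0.5 × √32.25 = 2.84 on 170 degrees of freedom, and the power of the two-sample t-test is 80.6%. At 42:126 it is 79.7%, so 43 is the smallest group that reaches 80%. Then 43 / 0.20 = 215. The plan's figure reproduces.

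**2. How many events are removed.** 215 − 43 − 129 = 43. That is 43/215 = 20% of usable events and 43/172 = 25% of those without a 30-day readmission.

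**3. The 30-day contrast with these events kept (43 versus 172).** With f = 43/172 = 0.25:

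- raw difference = 0.5 − f × m × 0.5
- comparator variance v = 1 + f(1 − f)(0.5m)²
- pooled SD = √[(42 + 171v)/213]
- d = raw difference / pooled SD
- overstatement = 0.5/d − 1

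For m = 0.5: raw difference 0.4375, v = 1.0117, pooled SD 1.0047, d = 0.4355, overstatement 14.8%.

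| m | d, 30-day contrast | Overstatement by the planned contrast | Power at 43:172 |
|---|---|---|---|
| 0 | 0.500 | 0% | 83.1% |
| 0.25 | 0.468 | 7% | 78.0% |
| 0.50 | 0.435 | 15% | 72.0% |
| 0.75 | 0.402 | 24% | 65.1% |
| 1 | 0.368 | 36% | 57.5% |

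If the removed subjects lay on the far side of the no-readmission group (m = −0.5), the sign would reverse: d = 0.56, and the planned contrast would understate by 11%.

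**4. Sensitivity to the share removed.** The 20% share is implied by the 3:1 ratio and is not stated as a rate. Holding 43 readmitted and 172 not readmitted by day 30, the overstatement is:

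| Share of the 215 removed | m = 0.25 | m = 0.50 | m = 0.75 |
|---|---|---|---|
| 5% | 2% | 3% | 5% |
| 10% | 3% | 7% | 11% |
| 15% | 5% | 11% | 17% |
| 20% | 7% | 15% | 24% |

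**5. A second model.** Take a normal latent risk, with the top 20% readmitted by day 30 and the next 20% in days 31 to 60, and a sensor correlated 0.2 to 0.4 with that risk. The standardized difference is then 17% to 18% larger with the exclusion than without it. The implied m is about 0.58, consistent with step 3.

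**6. Type I error.** If the sensor is unrelated to readmission at any time, removing subjects by readmission date does not select on the sensor. Simulated size at 43:129 is 5.1%.

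**The case against.** The exclusion is deliberate, disclosed and budgeted. It stands in the Synopsis and in three sections of the body, and the 3:1 ratio is built on it. Sections 10.1.1 and 10.6 declare the study exploratory, with no formal hypotheses and no efficacy claims. Leaving a gap between early readmissions and clear non-readmissions is a recognizable way to sharpen a contrast. An analysis with the events kept may stand in the separate statistical analysis plan. All of this is fair and limits the consequence. It does not remove the mismatch: the protocol itself fixes the exclusion in the primary analysis while describing the comparison as with versus without a 30-day readmission. In an exploratory study the estimate is the main product, so its label matters.

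A reader might infer four stronger things that the documents do not support:

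- **That the result will be overstated.** This depends on m, which is unknown. A small m is plausible: 5.1 counts readmission for any cause, and 3.1 says about three in four hospitalizations in HF patients are classified as unrelated to HF.
- **That the test or its stated power is wrong.** Neither is, for the contrast as planned (steps 1 and 6).
- **That the 43 events are recruitment that could be saved.** Enrollment is driven by the need for enough 30-day readmissions. With the events kept and m = 0, 40:160 gives 80.4% power, so 200 usable events would replace 215. At m of 0.25 or more, power at 215 falls below 80%, so the 30-day contrast would need more events, not fewer. The removed events also still serve phenomapping (10.5.2).
- **That this is a comparison of extremes.** Readmissions after day 60 stay in the comparator.

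**Conclusion.** The point holds as a mismatch between the stated and the tested contrast. Followed exactly, the plan estimates 30-day readmission versus no readmission to day 60, not 30-day readmission versus none by day 30. On the planning figures, 20% of usable events are removed. The overstatement is nil if the removed subjects resemble the no-readmission group, and about 7% to 24% if they carry a quarter to three quarters of the shift; it is smaller if fewer than 20% are removed. These sizes rest on an assumed sensor mean for the 31-to-60-day group and on the share implied by 3:1.

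The exclusion is also not defined consistently. The window starts at day 31 in 10.1.2 and 10.1.3 but at day 30 in 10.5.1, where it overlaps the 30-day group. The event is a readmission in 10.1.2 and an HF hospitalization in 10.1.3 and 10.5.1. Read literally, the latter could also remove a subject who was readmitted within 30 days and had a later HF hospitalization in the window. The count of 43 follows only from the form in 10.1.2.

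**What to change.** In 10.1.3 and 10.5.1:

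1. Report the difference between index events with a 30-day readmission and all usable index events without one, as the estimate for the stated objective.
2. Keep the present comparison beside it, labelled as 30-day readmission versus no readmission to day 60.
3. Give the window and the excluded event one definition, used alike in the Synopsis, 10.1.2, 10.1.3 and 10.5.1, and say that the exclusion applies to the comparator only.
4. Leave the 80% power statement attached to the present contrast. For the 30-day contrast, give 83% if the effect is undiluted and about 78%, 72% or 65% at m = 0.25, 0.50 or 0.75.

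The cost is wording. No new data or visits are needed, and 10.13 already provides for changes documented before the analysis. The downside is that the estimate for the objective may be smaller than the enriched one and may have less than 80% power at 215 events.
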